3.2 Rationale of study design

The open label, adaptive gene therapy trial design is intended to assess the safety, tolerability and efficacy of a single dose of CGF166. The trial design uses a staggered patient enrollment with continuous data reviews to limit as much unforeseen risk as possible prior to enrolling each patient in Part A or initiating another cohort in Part B, while also allowing for a potential clinical benefit. In addition, the trial design uses a sequential three Part design (Part A - Safety; Part B - Volume escalation; Part C - Efficacy) with cohort safety data reviews as described above. Based on the preliminary review of the data including changes observed in audiometry for patients from Cohort 1 through Cohort 4, the DSMB endorsed the team's proposal that 30 μ L is the maximum tolerated dose (volume) and start the Part C of the study.

3.3 Rationale of dose/regimen, duration of treatment

As a gene therapy that requires surgical administration, this will be a single dose study to assess the safety and tolerability as well as efficacy of CGF166.

Commercially Confidential Information

3.4 Rationale for choice of comparator

Not applicable.

3.5 **Purpose and timing of interim analyses / design adaptations**

3.6 Risks and benefits

3.6.1 Risks of clinical assessments

Magnetic resonance imaging with contrast will be performed during the course of this study. Common risks associated with MRI include interference with implanted metallic objects and there is a risk nephrogenic systemic fibrosis in patients with severe renal impairment who receive gadolinium. Accordingly, these patients must be excluded from this study. Some of the vestibular assessments may provoke nausea, vomiting and disequilibrium; these symptoms should be anticipated and managed expectantly.

3.6.2 Risks of general anesthesia and stapedotomy surgery

Foreseeable risks for the administration of CGF166 are largely those known for general anesthesia, which are uncommon, and those associated with modern stapedotomy.

In published series that describe stapedotomy outcomes, many patients experience transient vestibular symptoms that are procedure-related including dizziness and nausea. Post-operatively, it is possible that symptoms and signs of vestibular dysfunction may be more frequent or more severe than are usually observed after stapedotomy, or may persist for a longer period of time. Strategies to avoid patient Valsalva maneuvers and possible effects on the stapedotomy plug or the re-positioned tympanic membrane are important. Such preemptive approaches might include treatment with dexamethasone and anti-histamines, for example.

Known surgical risks of mild to moderate severity include persistent alteration of taste due to injury of the chorda tympani, infectious otitis media, perilymph fistula, reparative granuloma and perforation of the tympanic membrane, and worsened hearing. Each of the foregoing items carries a risk of 5% or less. Rare, but more serious adverse effects include facial nerve palsy, infective labyrinthitis or meningitis.

3.6.3 Risks of administering volume and CGF166 into the inner ear

Commercially Confidential Information

3.6.4 Potential benefits of CGF166 administration

Potential clinical benefits envisioned include improved hearing that may manifest as improved speech recognition and the ability to benefit from a hearing aid and avoid the need for a cochlear implant. Hearing correction achieved by the stapedotomy procedure often improves tinnitus in otosclerosis patients who have a post-operative improvement in their air-bone gap, so for those patients with tinnitus, it's possible that CGF166 therapy could improve the severity of their tinnitus too.

Commercially Confidential Information

For more details please refer to the Investigator Brochure.

4 Population

The study population will be comprise of patients who have severe-to-profound bilateral hearing loss or unilateral hearing loss with intact vestibular function in the non-operative ear. Patients are required to have documented non-fluctuating severe-to-profound hearing loss prior to enrollment. Up to 22 patients will be enrolled in the trial.

The investigator must ensure that all patients being considered for the study meet the following eligibility criteria. No additional criteria should be applied by the investigator, in order that the study population will be representative of all eligible patients.

Patient selection is to be established by checking through all inclusion/exclusion criteria at screening and baseline. A relevant record (e.g., checklist) of the eligibility criteria must be stored with the source documentation at the study site.

Deviation from any entry criterion excludes a patient from enrollment into the study.

4.1 Inclusion criteria

Patients eligible for inclusion in this study have to fulfill **all** of the following criteria:

- 1. Written informed consent must be obtained before any assessment is performed.
- 2. For all Parts (A, B and C) of the study, male or female patients, 18 to 75 years old, inclusive, with severe-to-profound bilateral or unilateral hearing loss with intact vestibular function. Non-fluctuating severe-to-profound hearing loss is required for the study ear and is defined as:

Confidential

- PTA within 10 dB of the PTA obtained at least 11 months previously.
- Word recognition within 20% of previous test at least 11 months previously [AAO-HNS Hearing Classification System]
- 3. Candidate ear ("study ear"): Minimal residual hearing based on the pure tone average of 0.5, 1, 2, and 4 kHz thresholds of ≤110 dB HL
- 4. Candidate ear ("study ear"): Pure tone audiometric thresholds of ≥50 dB HL for each testable octave frequency of 0.125 and 0.250 kHz, ≥ 70 dB HL for each testable octave frequency from 0.5 through 8 kHz and sentence recognition scores ≤50% at screening. Subject responses will be monitored for vibrotactile sensation, particularly for the low-frequency stimuli (e.g., 125 and 250 Hz). A frequency that elicits vibrotactile responses at levels below 70 dB HL will be considered "not testable" for hearing threshold and only those frequencies that are testable for hearing threshold will be considered for patient inclusion/exclusion in the study.
- 5. Patients with intact vestibular function in at least one ear (non-study ear) as measured by vestibular evoked myogenic potential (VEMP)
- 6. Able to communicate well with the investigator, to understand and comply with the requirements of the study
- 7. Meet surgical requirements/eligibility (including MRI scan within 3 months or at screening to confirm suitability for inner ear surgery)
- 8. Patients must weigh at least 40 kg to participate in the study, and must have a body mass index (BMI) <45 kg/m². BMI = Body weight (kg) / [Height (m)]²

4.2 Exclusion criteria

Patients fulfilling **any** of the following criteria are not eligible for inclusion in this study:

- 1. Use of other investigational drugs at the time of enrollment, or within 5 half-lives of enrollment, or until the expected PD effect has returned to baseline, whichever is longer; or longer if required by local regulations.
- 2. History of hypersensitivity to any of the study drugs or to drugs of similar chemical classes.
- 3. Patients with hearing loss caused by genetic/developmental disorders, e.g., cochlea aplasia.
- 4. Patients with existing conductive hearing loss or mixed hearing loss as judged by the Principal Investigator following a thorough review of all of the trial hearing assessments, air-bone gap assessment based on air and bone pure tone audiometry and MRI scan.
- 5. Patients with a history of cochlear implant in the study ear.

- 6. Hearing loss due to any other cause that would not be expected to respond to hair cell regeneration, for example trauma or central auditory lesions or lack of an auditory nerve
- 7. Patients who will require ototoxic drugs as routine therapy over the course of the study, for example cystic fibrosis patients.
- 8. Any contraindication to the planned surgery or anesthesia as determined by the surgeon, anesthesiologist, or designee.
- 9. Women of child-bearing potential, defined as all women physiologically capable of becoming pregnant, unless they are using highly effective methods of contraception during dosing and for 6 months following treatment period of the investigational medication. *Highly effective contraception methods include:*
 - Total abstinence (when this is in line with the preferred and usual lifestyle of the subject. Periodic abstinence (e.g., calendar, ovulation, symptothermal, post-ovulation methods) and withdrawal are not acceptable methods of contraception.
 - Female sterilization (have had surgical bilateral oophorectomy with or without hysterectomy) or tubal ligation at least six weeks before taking study treatment. In case of oophorectomy alone, only when the reproductive status of the woman has been confirmed by follow up hormone level assessment.
 - Male sterilization (at least 6 months prior to screening). For female subjects on the study the vasectomized male partner should be the sole partner for that subject.
 - Combination of any two of the following (a+b or a+c, or b+c):
 - a. Use of oral, injected or implanted hormonal methods of contraception or other forms of hormonal contraception that have comparable efficacy (failure rate <1%), for example hormone vaginal ring or transdermal hormone contraception.
 - b. Placement of an intrauterine device (IUD) or intrauterine system (IUS).
 - c. Barrier methods of contraception: Condom or Occlusive cap (diaphragm or cervical/vault caps) with spermicidal foam/gel/film/cream/vaginal suppository.
 In case of use of oral contraception women should have been stabile on the same pill for a minimum of 3 months before taking study treatment.
- 10. Sexually active males must use a condom during intercourse after investigational drug treatment and for 6 months after stopping investigational medication and should not father a child in this period. A condom is required to be used also by vasectomized men in order to prevent delivery of the drug via seminal fluid.
- 11. Bilateral cochlear implants or a past attempt for cochlear implant in the study ear or any other inner ear surgery that could interfere with drug efficacy.
- 12. Any other otologic history, including but not limited to chronic otitis, cholesteatoma, tympanic membrane perforation, head and neck radiation or Meniere's disease, that suggests poor candidacy for cochlear implant or inner ear surgery or suggests potential interference with study auditory or vestibular function tests.
- 13. Abnormal vital signs and/or ECG that suggest potential contraindication for planned study anesthesia or past serious adverse reaction to anesthesia.
- 14. Patients with estimated glomerular filtration rate (GFR) < 30 ml/min (MDRD formula) at screening.
- 15. Patients with heart failure NYHA class III or IV.

- 16. Patients with Child-Pugh class C cirrhosis.
- 17. History of myocardial infarction, coronary bypass surgery, or any percutaneous coronary intervention (PCI) within 6 months prior to screening.
- 18. Patients who require chronic anticoagulation, except daily aspirin.
- 19. A psychiatric disease or substance abuse history likely to interfere with protocol compliance.
- 20. Any medical condition, judged by the investigator, that is likely to interfere with the patient's participation in the study, or likely to cause serious adverse events during the study.
- 21. Pregnant or nursing (lactating) women, where pregnancy is defined as the state of a female after conception and until the termination of gestation, confirmed by a positive hCG laboratory test.
- 22. Immunocompromised patients, as judged by the investigators based on patient history, physical exam and CBC

No additional exclusions may be applied by the investigator, in order to ensure that the study population will be representative of all eligible patients.

5 Treatment

5.1 Protocol requested treatment

5.1.1 Investigational treatment

CGF166 is a recombinant adenovirus 5 (Ad5) vector containing the human Atonal transcription factor (Hath1) cDNA. Commercially Confidential Information

CGF166 will be delivered using an infusion pump system with a blunt needle cannula (as per the Surgical and Pharmacy/Drug Delivery Manuals details provided separately).

Commercially Confidential Information

5.1.2 Additional study treatment

No additional treatment beyond investigational treatment is requested for this trial.

5.2 Treatment arms

Patients will be assigned to one of the 5 cohorts. Part A and Part B of the study have been completed; dose volumes administered reflect the study treatment for each cohort including planned dose volume for Part C of the study (see Table 5-1 for estimated viral particle delivery quantity and normalized doses estimates).

Study treatments are defined as:

- Part A:
 - Cohort 1: single dose of 20 µL CGF166
- Part B:
 - Cohort 2: single dose of 40 or 30 µL CGF166
 - Cohort 3: single dose of 40 µL CGF166
 - Cohort 4: single dose of 60 µL CGF166
- Part C:
 - Cohort 5: single dose of 30 µL @ 10 µL/minCGF166

Commercially Confidential Information

Confidential

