	The current study will evaluate the safety, tolerability, and potential efficacy of CGF166 and the associated delivery procedures in patients with severe-to- profound bilateral or unilateral hearing loss with intact vestibular function in the non-operative ear. Patients are required to have documented non-fluctuating hearing loss.
	Part A
	Part A will include a safety and tolerability cohort (N=3). Patient dosing will be staggered; dosing the next patient in a cohort will be based on a safety data review including all data available through 4 weeks post-dose of the previously dosed patient(s).
	Part B
	Part B will include a volumetric escalation design to evaluate infusion volumes of the same CGF166 concentration Confidential Information in 3 cohorts of patients (n=3/cohort; total of 9 patients).
	Each subsequent cohort will be dosed only after the volume delivered in the prior cohort is deemed to be safe and tolerable as determined by the dose safety review meeting based on safety data review of the complete previous cohort including all data through 4 weeks post-dose.
	Safety review meetings will be organized to evaluate available safety data and to determine if it is appropriate to escalate to the next infusion volume.
	Part C
	Based on the DSMB review of data from Part A and Part B of the study, Part C of the study will administer a dose volume of 30 μ L at the rate of 10 μ L/min. A total of 10 patients will be enrolled in Part C of the study.
Population	 Patients with severe-to-profound bilateral or unilateral hearing loss with intact vestibular function in the non-operative ear
	 Adult patients who are candidates for a cochlear implant

Confidential

Inclusion criteria	 For all Parts A, B and C of the study, male or female patients, 18 to 75 years old, inclusive, with severe-to-profound bilateral hearing loss or unilateral hearing loss with intact vestibular function in the non- operative ear. Non-fluctuating severe-to-profound hearing loss is required for the study ear and is defined as:
	 Pure-tone average (PTA) within 10 dB of the PTA obtained at least 11 months previously
	 Word recognition within 20% of previous test at least 11 months previously
	 Candidate ear ("study ear"): Minimal residual hearing based on the pure tone average of 0.5, 1, 2, and 4 kHz thresholds of ≤110 dB HL.

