Investigational and reference therapy	 CGF166 is recombinant adenovirus 5 (Ad5) vector containing the human Atonal transcription factor (Hath1) cDNA. CGF166 will be provided in a septum vial, containing 0.5 mL Commercially of opalescent liquid viral vector. In Part A and Part B all investigational infusion volume was infused at a rate of 10 µL/min except 1 patient where in fusion volume was infused at a rate of 20 µL/min. In Part C all following protocol amendment 5 all investigational infusion volumes will be infused at a rate of up to 10 µL/min in to the perilymphatic space 						
Efficacy	litory assessments						
assessments	 Pure tone audiometry, including immittance testing Speech audiometry Brainstem auditory evoked response evaluations (BAER) 						
	Vestibular assessments						
	Head Impulse test						
	Commercially Confidential Information						
Safety assessments	 Physical examination Otoscopy 						
	 Neurological exam FSH verification and Pregnancy test (serum at screening and urine at subsequent visits) 						
	 Vitals and body measurements (height, weight, temperature, blood pressure, and pulse rate) 						
	• ECG						
	Clinical laboratory tests (hematology, chemistry, and urinalysis)						
	MRI with gadolinium (within 3 months or performed at screening)						
	Adverse events						
Other assessments	Commercially Confidential Information						

Data analysis	 Tone thresholds will be analyzed for each frequency tested separately.
	 Pure tone audiometry air conduction threshold data will be listed and graphically displayed by patient, infusion volume, frequency, and visit/time.
	 Summary statistics will be provided by infusion volume, frequency, ear and visit/time.
	 Change from baseline of the thresholds (mean of screening and baseline visit) will also be summarized by infusion volume, frequency, ear and visit/time
Key words	Hearing loss, cochlear implant, gene therapy

Assessment schedule

Study Phase	Screening visit	Baseline	Treatm ent day	Post-op O	bserv	ation	period			Follow -u				End of Study⁵
	Day -63 to -4	Day -3 to -1		Day 1			Day 4	Day 6	Day 15	Day 29	Day 57	Day 113	Day 169	
Visit Num bers	1	2		3		4	5	6	7	8	9	11	13 / 777	777
Time (h)			pre-infusion	Post-infustion	4 hr									
Inclusion/Exclusion	x	x												
Relevant medical history/Current medical conditions	x	x				as needed								
Demography	х													
Auditory and vestibular function assessments	x	x								x	x	x	x	x
	Con	nmercially C	confidential Info	ormation										

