3.1 Study design

This non-confirmatory three part study utilizes an open label, single dose, sequential cohort design for the investigation of CGF166 and will be conducted in multiple centers.

The current study will evaluate the safety, tolerability, and potential efficacy of CGF166 and the associated delivery procedures in patients with severe-to-profound bilateral or unilateral hearing loss with intact vestibular function in the non-operative ear. Patients are required to have documented non-fluctuating severe-to-profound bilateral or unilateral hearing loss prior to enrollment. A maximum of 22 patients will be enrolled in this 3 Part, 5 cohort trial (Figure 3-1).

Novartis Amended Protocol Version v06 (Clean) Confidential

Page 40 Protocol No. CCGF166X2201

Part A

Part A will assess the safety and tolerability as well as potential efficacy following a single IL dose of 20 uL of CGF166 concentration Commercially Confidential Patient enrollment will be staggered so that a safety data review can be done after each treated patient (~4 weeks after treatment) prior to dosing each subsequent patient.

Part B

Part B will include a volumetric escalation design to evaluate up to 3 infusion volumes (between 20 and 60 μ L) of the same CGF166 concentration^{Commercially Confidential} 3 cohorts of patients (n=3/cohort; total of 9 patients). All dose volumes are subject to change based on trial safety data.

Each subsequent cohort will be dosed only after the volume delivered in the prior cohort is deemed to be safe and tolerable as determined by the Drug Safety Monitoring board (DSMB). The DSMB will consist of internal Novartis personnel as well as at least one external subject matter expert who is not serving as an investigator or otherwise privy to trial data. The membership and workings of the DSMB will be detailed in the DSMB Charter. In addition, the scheduling and dosing of the first patient in each cohort will be staggered to allow at least a four week interval in between treating the remaining 2 patients in each cohort.

Part C

Considering the preliminary overall review of the data including changes observed in audiometry for patients from Cohort 1 through Cohort 4, the DSMB endorsed the team's proposal that $30 \ \mu L$ is the maximum tolerated dose (volume) observed in the study.

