The highest safe and tolerable volume determined in Part B will be used for IL-infusion in Part C patients. A total of 10 patients will be required for Part C of the current study. A safety review analogous to that described for parts A and B will take place whenever a block of five patients completes the first 4 weeks of study assessments.

Part A-C

Patients will undergo the same protocol-required assessments and visit schedule in all Parts of the trial (A-C). Part C of the study will only commence once preliminary safety and tolerability has been established for CGF166 and the associated delivery methods in patients in Part A and B.

The trial duration will consist of 63 day screening period followed by a 1-3 day baseline assessment period and in house surgical dose/post operation assessment period (~6-14 days) followed by a 6 month post-dose assessment period. In addition, all dosed patients in all Parts A-C will be advised of the opportunity to enroll in a separate protocol Commercially Confidential Information

During the screening period, eligibility of potential patients will be verified at the study centers.

Potential patients will be evaluated for fitness to undergoing protocol-required surgery and for the planned therapy based on physical exam, MRI, past/current medical history, and laboratory testing. During the screening period, potential patients will also undergo pre-treatment^{Commercially}, auditory and vestibular function tests.

At least two outpatient visits during the screening period are anticipated in order to complete the required verification and assessments. If all screening assessments can be completed in one visit, that is allowed. Additional outpatient screening visits (i.e., more than 2 visits) are permitted pending patients' and clinic schedule and the need for re-verifications and potential re-testing.

Based on the screening assessments, one ear will be selected as the study ear and will undergo the study required surgery; criteria for the selection of the study ear are described as follow:

- The ear with more severe hearing loss as determined by pure tone audiometry and speech recognition score
- If both ears have equal severity in hearing loss, then the study ear will be selected by the investigator's preference

Upon completing the screening visits, eligible patients will be scheduled for a baseline visit and surgery.

Baseline (Day -3 to -1)

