9.4.2 Statistical model, hypothesis, and method of analysis

Tone thresholds will be analyzed for each frequency tested separately.

For pure tone audiometry, a measure that depends on a patient being able to hear a tone, the following imputation will be done: If a patient is unable to hear the tone at a specific frequency it can be inferred that the threshold value exceeds the upper limit of the machine. In this case the value will be imputed to 5dB above the upper limit of the machine.

All pure tone audiometry air conduction threshold data will be listed and graphically displayed by patient, infusion volume, frequency, and visit/time. Summary statistics will be provided by infusion volume, frequency, ear and visit/time. Change from baseline of the thresholds (mean of screening and baseline visit) will also be summarized by infusion volume, frequency, ear and visit/time.

In addition, safety and tolerability is a co-primary endpoint, and will be analyzed as in Section 9.5.2 (Safety).

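### Grouping by infusion volume alone puts Cohort 2's 30 µL patients, whose audiometry informed the choice of 30 µL, in one row with Part C; Cohort 5 should also be shown alone

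*Protocol*

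**What the plan says.** Protocol Section 5.2 says that Parts A and B are complete and lists the volumes administered: 20 µL in Cohort 1, "Cohort 2: single dose of 40 or 30" µL, 40 µL in Cohort 3 and 60 µL in Cohort 4. The Part C entry is "Cohort 5: single dose of 30" µL. How many of the three Cohort 2 patients received each volume is not stated.

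Section 3.2 explains the choice: "Based on the preliminary review of the data including changes observed in audiometry for patients from Cohort 1 through Cohort 4", the DSMB endorsed 30 µL as the maximum tolerated volume and the start of Part C. Section 3.1 gives the same account. Section 3.2 labels Part C the efficacy part.

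For the primary variable, Section 9.4.2 states: "Summary statistics will be provided by infusion volume, frequency, ear and visit/time". Change from baseline is grouped the same way, and the synopsis agrees. Cohort, Part and infusion rate are not grouping factors.

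The visible text of SAP 7.1.2 lists and plots thresholds by patient and volume and gives no summary statistics for them. SAP 8.1 tabulates adverse events by infusion volume where applicable. Protocol 9.5.2 tabulates them by treatment, and Section 5.2 defines study treatments Part by Part and cohort by cohort.

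On rate, the synopsis says that Parts A and B were infused at 10 µL/min "except 1 patient where in fusion volume was infused at a rate of 20" µL/min. That patient's cohort and volume are not given.

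**The concern.** Part C is where the plan looks for efficacy at the chosen volume. A reader will take the 30 µL row as its result. That row, as specified, also holds patients whose primary-variable data were reviewed when 30 µL was chosen. If 30 µL was favoured partly because those patients did comparatively well, their results lean in its favour by chance, and pooling carries some of that into the row. No summary of the 10 Part C patients alone is specified in the visible text.

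The two documents may also place the same patient differently for safety. A Cohort 2 patient given 30 µL sits with Part C under the SAP's grouping. Under the protocol's grouping the same patient can be read as belonging to Cohort 2. Safety and tolerability is itself a primary objective, so this needs settling whatever the size of any bias.

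Finally, a table grouped by volume does not mark the patient infused at the different rate.

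**Working it through.** **Enrolment.** Part A has 3 patients (synopsis), Part B has 3 × 3 = 9 (Section 3.1), and for Part C Section 3.1 says "A total of 10 patients will be required for Part C of the current study". The sum 3 + 9 + 10 = 22 reproduces the maximum in Section 3.1.

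**Make-up of the rows.** Let k be the number of Cohort 2 patients given 30 µL. Section 5.2 reports volumes administered and names both, so with three patients k is 1 or 2.

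- 30 µL row: 10 + k patients, of whom k/(10 + k) come from Cohort 2. For k = 1, 1/11 = 9.1%; for k = 2, 2/12 = 16.7%.
- 40 µL row: 3 from Cohort 3 plus 3 − k from Cohort 2, that is 5 or 4 patients.

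**Illustrative selection effect.** The documents give neither an SD of change nor a numerical selection rule, so both are assumed. The model has equal true mean change at all volumes, a between-patient SD of 1, and 3, k, 6 − k and 3 patients at 20, 30, 40 and 60 µL. It keeps the runs in which 30 µL looked better than its comparators (400,000 runs before selection). If b is the resulting bias in the k patients, then

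pooled bias = b × k/(10 + k),

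because Cohort 5 was treated after the choice and contributes zero. Results in SD units:

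| 30 µL looked better than | k = 1: b | k = 1: pooled | k = 2: b | k = 2: pooled |
|---|---|---|---|---|
| 40 µL | 0.727 | 0.066 | 0.462 | 0.077 |
| 40 and 60 µL | 0.897 | 0.081 | 0.628 | 0.105 |
| all other volumes | 1.004 | 0.091 | 0.734 | 0.123 |

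The first line has a closed form, b = √(2/π) × V30/√(V30 + V40), where V is the variance of the group mean. For k = 1, V30 = 1 and V40 = 1/5, so b = 0.798/√1.2 = 0.728. For k = 2, V30 = 1/2 and V40 = 1/4, so b = 0.798 × 0.5/√0.75 = 0.461. Both agree with the simulation. Cohort 5 alone showed a bias of 0.00 SD under every rule.

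**Scale.** For assumed SDs of 5, 10 and 15 dB, the pooled bias over k = 1 to 2 is about 0.3 to 0.6, 0.7 to 1.2 and 1.0 to 1.8 dB. The standard error of a 10-patient mean is 1/√10 = 0.316 SD, so the bias is 0.066/0.316 = 0.21 to 0.123/0.316 = 0.39 of a standard error. Inclusion criterion 2 accepts a PTA within 10 dB of the earlier value as non-fluctuating.

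**The case against.** The case for leaving the plan alone is substantial.

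- **Grouping by volume received is ordinary practice.** Section 9.1 analyses patients by treatment received, Part B holds the concentration constant, and Section 3.1 applies the same assessments in all Parts. This stands, and it is why the by-volume table should stay. It does not supply a Part C summary.
- **The effect is small and nothing visible hinges on it.** The study is described as non-confirmatory, no test on thresholds is visible, and listings by patient would let a reader separate the cohorts. This stands too, though a listing does not replace a prespecified summary of the efficacy part.
- **The split may exist elsewhere.** Parts of the SAP are redacted, and table shells are in a separate module that is not available. This cannot be checked.

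A reader might also infer more than the documents support:

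- **That the Part C result itself is biased, or that patients were selected on outcome.** A volume was chosen, not patients, and Cohort 5 was treated afterwards. Only the pooled row is affected.
- **That 30 µL was the best-looking volume.** The protocol calls it the maximum tolerated volume. Under such a rule 20 µL could look better and still not be chosen. Audiometry also serves as a safety measure (Section 6.5.6), so some selection on it is plausible, but its size cannot be derived.
- **That the 30 µL row mixes infusion rates.** The volume given to the 20 µL/min patient is not stated. What follows is only that this patient is unmarked in some volume row.
- **That the SAP specifies a pooled mean change in threshold.** Its visible text does not; that pooling comes from the protocol.

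**Conclusion.** The point holds for the pooled 30 µL row. As written, the protocol's threshold summaries and the SAP's adverse event tables combine at least one Cohort 2 patient, whose audiometry was in the review behind the volume choice, with the 10 Part C patients. No Part C summary is visible. The row's lack of independence follows from the text alone.

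Its size does not. About 0.07 to 0.12 SD assumes 1 or 2 affected patients, equal true means and selection on a favourable mean change. The dB figures add an assumed SD. The model covers threshold change only and says nothing about the direction of any effect on adverse event rates. This is a modest reporting weakness in a non-confirmatory study, worth correcting because the correction is cheap. The differing safety groupings in the two documents are a separate inconsistency that needs resolving in any case.

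**What to change.** - In Protocol 9.4.2, in SAP 7.1.2 if threshold summaries are produced, and in SAP 8.1, present Part C (Cohort 5) on its own as the Part C estimate.
- Keep the by-volume table as a supportive display. Flag in it the Cohort 2 patients given 30 µL and the patient infused at 20 µL/min, and state how many Cohort 2 patients received each volume.
- Reconcile the safety grouping in Protocol 9.5.2 (treatment) with SAP 8.1 (infusion volume), and say whether treatment means cohort or volume.
- Reconcile the Part C infusion rate, which the synopsis gives as an upper limit of 10 µL/min and Section 5.2 as 10 µL/min, so that any flag by rate has a clear reference.

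The cost is one grouping variable, an extra row or table, and no new data. Leaving out 1 or 2 patients widens the standard error of the Part C mean by a factor of √(11/10) = 1.05 or √(12/10) = 1.10. The visible SAP still describes four Part B cohorts and 20 to 30 Part C patients, and SAP 1.2 calls for a new version when a design change affects the methodology before database lock. The correction can go into that version.
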